## 2. STUDY PROTOCOL

[figure not shown]
### 2.1 Background and Significance

#### *Background:*

Coronavirus disease 2019 (COVID-19) is a highly contagious virus transmitted via respiratory secretions and was established as a pandemic on March 11, 2020. The severity of the disease ranges from asymptomatic/mild (81%), to severe requiring oxygen (14%) and critical (5%) which requires intensive care unit (ICU) admission, ventilation and life support. Two-thirds of these severe cases will develop the most severe manifestation of the disease, acute respiratory distress syndrome (ARDS). Various epidemiologic reports show that the greatest mortality and morbidity risks concern frail and vulnerable people, in particular the elderly, and patients who suffer from multiple comorbidities or chronic diseases (mainly hypertension, diabetes, cardiovascular disease, chronic, respiratory disease, immune compromised status). Patients requiring a stay in the ICU often have a considerably longer length of stay (LOS) than the typical ICU patient. At Barnes-Jewish Hospital (BJH) the typical LOS for an intubated ICU patient with COVID-19 disease is 10-12 days, whereas a non-COVID-19 medical ICU patient is 3-4 days. Thus far, the greatest attention has been paid to strategies to control contagion diffusion and life-saving measures for these critically ill infected patients. It is now time to focus on the inevitable long-term consequences of surviving COVID-19 disease. This feasibility study will provide information not only regarding the long-term sequelae of COVID-19 disease, but also how to structure future care with a primary emphasis on telehealth, both of which may be important if society is faced with another highly contagious disease.

The patients that survive will likely suffer from secondary physical, cognitive and mental impairments due to their prolonged stay in the ICU. Together, these components comprise the Post Intensive Care Syndrome (PICS). PICS purportedly affects 50 – 70% of ICU survivors which may develop during their stay or after discharge and it is estimated one-third of these survivors will die within a year. Post COVID-19 patients may be at increased risk of PICS due to a prolonged period of respiratory distress and immobility along with the potential of lung fibrosis and cardiovascular

CONFIDENTIAL: This document is the intellectual property of [name]. Acceptance of this document constitutes the agreement by the recipient that no unpublished information contained herein will be published or disclosed without prior written approval.

deconditioning. In addition, unlike other patients with PICS, the survivors of COVID-19 may also find themselves facing distorted human relationships and social fabric within a changing economic picture, which may compound their mental health symptoms. The COVID-19 pandemic disease surge will create an unprecedented number of ICU survivors vulnerable to PICS in the upcoming months, generating a major public health issue.

It is imperative as a health system we determine multiple avenues to address the needs of these COVID-19 survivors. The findings from this study are the first steps in determining the feasibility and potential impact of a telehealth PICS clinic that is able to address the needs of patients with COVID-19 disease and potentially other patients that are unable to attend a brick and mortar clinic and require virtual care. This research will examine the feasibility, acceptance and potential impact of a multi-professional telehealth ICU recovery care platform in addressing the needs of discharged ICU patients with COVID-19 disease from the viewpoint of the patient, the primary care physician and clinic provider. These findings will advance our understanding of the ability to use telehealth to provide care in an environment of patient isolation, as well as to those who may have been discharged with suboptimal inpatient education.

[figure not shown]
### **2.1.1 Preliminary Data**

Although some evidence exists regarding the characteristics of inpatients with COVID-19 disease, it is far from robust. In addition, it is not clear what staff to inpatient interactions, such as frequency of therapy sessions or inpatient nursing education, were forgone due to the risk of viral contamination and need to preserve personal protection equipment. A Washington University IRB approved (#202005039) observational study at BJH will add to the COVID-19 body of literature on these topics and some of the pertinent data obtained will be used in the interpretation of results of the proposed study herein. Evidence regarding long-term complications of COVID-19 disease is lacking, however insights from PICS may provide a roadmap for the future care of these patients. It is highly likely, COVID-19 patients will suffer from similar physical, cognitive and mental health issues long-term.

The physical impairments associated with PICS are believed to stem from ICU acquired weakness (ICU-AW) which is a combination of polyneuropathy, myopathy, neuromyopathy and muscle deconditioning. Patients with PICS are reported to have poor mobility, frequent falls and a dramatic loss of independence with activities of daily living (ADLs). A study by Borges et. al. compared 72 patients with sepsis/septic shock to a healthy control group. The patients admitted to the ICU had a substantial reduction in physical activity, exercise capacity and muscle strength at 3 months post discharge. An evaluation of 109 ARDS patients, demonstrated that although there was an improvement in the six-minute walk test at 12 months, the results were still only 66% of predicted distance and only 49% of the patients had returned to work. These findings were confirmed in another study which found 69% of patients with PICS were still restricted in performing ADLs and 50% had not returned to work 12 months after discharge.

In addition to long lasting physical detriments, new or worsening impairments in cognitive

CONFIDENTIAL: This document is the intellectual property of [name]. Acceptance of this document constitutes the agreement by the recipient that no unpublished information contained herein will be published or disclosed without prior written approval.

function persist months to years after ICU discharge and are also associated with decrease ability to perform ADLs, as well as, reduced quality of life. There is strong evidence that patients with delirium while in the ICU may suffer from cognitive impairments long after they are discharged. Delirium is a common condition resulting from critical illness. This is particularly true in patients who require increased sedation and prone positioning to improve oxygenation, such as COVID-19 patients with ARDS. While receiving these medical interventions, patients often are unable to have clear memories leading to altered and sometimes frightening delusions from delirium.

Anxiety, post-traumatic stress disorder and depression (70%, 10-50%, and 30%, of survivors respectively) are the major mental illnesses noted in ICU survivors 12 months after discharge. Theoretically, these percentages may be even higher in patients with COVID-19 disease who may experience exacerbated feelings of emptiness, due to separation and isolation from family and friends, a breakdown of their social network, as well as the uncertainty about their diagnosis.

Prevention of PICS includes the incorporation of the ABCDEF bundle (assessment, prevention and management of pain; both spontaneous awakening and breathing trials; choice of analgesia and sedation; coordination of care and communication; delirium assessment, prevention and management; early mobility and exercise; and family engagement), widely known as the bundle that addresses the risks of sedation, delirium and immobility. Both inactivity and malnutrition may exacerbate ICU-AW through skeletal muscle mass, strength and function loss. ICU diaries completed by staff and family members for the patient provide a description of experiences during ICU care. The diary may help to prevent PICS by improving the orientation of the patient and alleviating anxiety, depression and PTSD symptoms.

Although individual symptoms of PICS have been reported over the past decade, PICS first became recognized in 2015. Often signs and symptoms of PICS do not manifest until the patient has returned home, requiring evaluation and treatment in the outpatient setting. A wide variety of follow-up strategies to prevent/limit the impairments associated with PICS for ICU survivors have been examined which include: communication of care between the ICU team and primary provider, peer support groups, follow-up phone-calls from the ICU staff to patient, and scheduled in-person consultations. There has also been the establishment of PICS outpatient clinics to attempt to manage this complex patient population. The goals of these clinics have been to improve recovery, decrease the cost burden on the healthcare system and improve the patient's quality of life. Unfortunately, very few outpatient PICS clinics currently exists and those that do are generally in metropolitan areas. However, according to the American Hospital Association approximately 80% of ICU beds are located in community hospitals, suggesting these clinic may not be easily accessible by the majority of patients who need them (<https://www.aha.org/statistics/fast-facts-us-hospitals>).

Services offered and clinical professionals available may vary from clinic to clinic. Most have a medical director specializing in PICS and nursing support. Other professionals may include some combination of a neuropsychologist, social worker, pharmacist, physical therapy, occupational therapy, case manager and dietitian. In clinics with limited professionals, services include the patient evaluation and then coordination of care with referrals to primary care, subspecialty services,

CONFIDENTIAL: This document is the intellectual property of [name]. Acceptance of this document constitutes the agreement by the recipient that no unpublished information contained herein will be published or disclosed without prior written approval.

physical and occupational therapy as needed. A review of 30 clinics demonstrated the majority were limited to physician and nurse interactions while incorporating patient self-evaluation tools. Most patients returned for their first clinic visit within six to twelve weeks after hospital discharge, although some initiated visits within 3 weeks.

Unfortunately, not all PICS outpatient clinics are widely utilized. Some authors report only 20-50% of patients discharged from the ICU suffering from symptoms, will seek follow-up care at a PICS clinic. For example, in a single center study, 34 discharged ICU patients demonstrated significant declines in mobility ( $p=0.026$ ), ADLs ( $p<0.001$ ) combined with increased anxiety/depression ( $p=0.048$ ), yet under half of them sought follow-up care. When asked why they were not accessing healthcare services the main reasons included: unclear how to obtain referral, unable to afford the service, and lack of physical strength or transport to get to the clinic. PICS patients often suffer from financial difficulties due to the inability to return to work, which may make it more difficult for them to travel to a clinic. However, like other patients they want to get better. Interviews of 39 adult critical illness survivors revealed the following core patient priorities during recovery: going home, improving mobility, participating in self-care, restoring physical and psychological health, and resuming previous roles and routines.

Discharged patients with COVID-19 disease may experience increased challenges with transportation and treatment at an “in-person” clinics due to current restrictions in place for public and healthcare worker protection.

[figure not shown]
## 2.2 Objective

- Evaluate discharged ICU COVID-19 patients’ involvement in, and acceptance with virtual CoV-PICS clinic visits.
- Test the design of a multi-professional telehealth outpatient CoV-PICS clinic for effective care processes that evaluate impairments in physical, cognitive and mental health function in patients with COVID-19 disease.
- Determine the feasibility and acceptance of Primary Care Physicians regarding information provided and communication process from the CoV-PICS clinic.
- Determine if the PICS symptoms experienced by COVID-19 patients are similar to historically reported symptoms in non-COVID 19 patients with PICS.

## 2.3 Patient Selection

Patients who are +COVID-19 with a stay in the ICU. This screening list (name, medical record number) will be provided by the PI for (IRB#202005039) study: “The Effects of COVID-19 on Nursing Indicators, Delirium, Nutritional Status and Functional Mobility”. The research coordinator will review the medical record for exclusion criteria, if none exist, and a contact phone number is available, the research coordinator will complete a phone screen (see attached).

CONFIDENTIAL: This document is the intellectual property of [name]. Acceptance of this document constitutes the agreement by the recipient that no unpublished information contained herein will be published or disclosed without prior written approval.

### **2.3.1 Inclusion Criteria**

1. Patients who are at least 18 years of age
2. COVID-19 diagnosis with a stay in the intensive care unit at BJH

### **2.3.2 Exclusion Criteria**

1. Severe cognitive deficits or dementia prior to hospitalization
2. Long-term resident of a skilled nursing facility prior to admission
3. Non-English speaking (will not have an interpreter available)
4. Hospice or Comfort Care at discharge
5. No plans to return to some degree of independent living at the time of discharge
6. Pregnant or a prisoner at the time of discharge
7. Blind or deaf

If during the consent process if it is determined the patient will not have a home internet connection or smartphone access for the virtual clinic; or displays the inability to use either a computer or phone for virtual appointments, they will also be excluded from enrollment.

[figure not shown]

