## **2.4. Study Design**

Observational feasibility. To determine if discharged COVID-19 patients with PICS symptoms are willing and able to navigate the technology necessary to participate in a virtual outpatient clinic. To determine if a multidisciplinary group of professionals, who are licensed in the state where the participant lives, familiar with PICS, are able to interpret information obtained from virtual visits and patient self-reported surveys to make recommendations for future care based on baseline and changes in patient symptoms over time. To determine the ease of receiving and receptiveness of primary care physicians to a summary of clinic recommendations. To determine if the PICS symptoms and patient characteristics of patients with an ICU stay due to COVID-19 are similar to those reported in the literature of non-COVID-19 patients.

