### **2.4.1 Study Procedures**

[figure not shown]
Study Procedures – Patient and PCP involvement	
Consent	Verbal consent is being sought. RC will be in a private space and obtain consent. All visits with the patient will be “virtual”.
Chart Review	Once patient consent is obtained, a prospective or retrospective chart review (depending on availability of research team members) will be conducted to obtain several data points (see attached).
Day 1	RC: Add patient to enrollment log: Study ID, first name, 3 letters of last name, MRN#, hospital discharge date, date returned home (if different from discharge date), and patient preferred email and phone number. If patient consents, PCP name, office phone number and fax number. This will be in a password protected Excel file available only to research team members.
Day 1	RC: Document date/time of consent, upload pdf of note to RedCap

CONFIDENTIAL: This document is the intellectual property of [name]. Acceptance of this document constitutes the agreement by the recipient that no unpublished information contained herein will be published or disclosed without prior written approval.

[figure not shown]
Day 1	
RC: Patient emailed a copy of the verbal consent, as well as, an information sheet, including a timeline for the study and “what to expect” and “what not to expect”.
 
What to expect: Timeline for study, Initial surveys, follow up surveys at 3 and 6 months, team visits (when – at minimum every 12 weeks; time commitment – 60-75 minutes), bi-weekly touch base email by RCs, individual visits with team members if warranted, summary of team recommendations after each visit, potential contact from PCP (if patient consented for information to be shared) and contact information for RC and PI for any questions or concerns throughout the study period. All providers engaging in telehealth visits will be licensed in the state where the participant lives.
 
What not to expect: Clinic physicians or other providers to write prescriptions, order lab tests or perform any treatments

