Day 1-2  Week 10 post initial visit And Week 22 post initial visit	
RC: If patient not enrolled in MyChart or has forgotten how to access, call patient and walk them through obtaining access. Direct link (attached to the patient’s study ID) will be emailed or texted (per patient preference) to access the following surveys, requesting one week turn-around time:
 
ICU Memory Tool® (measures recall and aids in our understanding of quality of life)
 
PROMIS®29 Profile (measures anxiety, depression, fatigue, pain, physical function, sleep and ability to participate in social roles)
 
MOCA-5 minute® (measures cognitive function)
 
PG-SGA short form® (screens for malnutrition risk)

Day 2-9  Week 11 and Week 23 post initial visit	
RC: Will send form email from PI to PCP (if patient agreed to share information) providing an overview of the study (see attached)
 
RC will obtain notice from RedCap when surveys opened. RC will check completeness of survey responses. If surveys not completed within 5 days, send reminder email. If not completed in 7 days, call patient offering to administer surveys over the phone.

Day 11  Week 11 and Week 23 post initial visit	
RC: If patient does not complete surveys within 7 days of receipt and has not responded to phone calls; considered an enrollment fail (start of study) or withdrawal from study (repeat surveys), document on enrollment log.

Day 2-11  Week 11 and Week 23 post initial visit	
RC: If surveys completed, send thank you email. Email and/or call patient to schedule first virtual visit. Email link to research team members for them to review responses in RedCap.

Day 9 – 18  Week 12 and Week 24 post initial visit	
RC: Schedule initial 60-75 minute virtual assessment based on MD schedule. Email all team members to obtain availability in non-physician visit time. Send outlook calendar appointments to team members. All providers engaging in telehealth visits will be licensed in the state where the participant lives.

1-2 days before virtual team visit	
RC: Send reminder email to research team members who will be on the visit. Send agenda for call – member/time slot. Send instructions/link for team members to join the virtual visit. Email the patient the instructions on how to access the virtual appointment in MyChart or the HIPPA approved WashU ZOOM link.

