## **2.4.3 Pre-Study Period**

## **2.4.4 Study Period**

### **Methods:**

## **2.4.6 Observations and Measurements**

### **2.4.6.3 Primary Outcome Measures**

Primary outcomes:

1. Patient adherence and determination of feasibility and acceptance with the virtual clinic and telehealth visits based on the FIM® (feasibility of intervention measure), IAM® (intervention appropriateness measure) and the AIM® (acceptance of intervention measure)
2. Patient attendance record
3. Number of on-time arrivals to the virtual visit
4. Number of patient successfully completed online questionnaires after initial training.
5. Patient primary care or clinic physician feedback using the tools in #1 and open ended comments.

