#### **2.4.6.6 Sample Size**

A consensus sample would be optimal in this feasibility study (all patients meeting criteria consented and participated), however since that is unlikely, a convenience sample will be used. The future of patients with COVID-19 disease requiring ICU admission is uncertain. A conservative estimate of 50% of these patients will develop PICS. In the first month at BJH, 29 patients were discharged from the ICU. This translates into approximately 15 patients per month. Although this number may increase or decrease due to uncertainties surrounding the disease. Previous studies (see literature review) suggest care for PICS should begin within 12 weeks of discharge. Therefore once IRB approval is obtained, patients discharged within the past 10 weeks will be screened for possible participation. A post-hoc power analysis will be done.

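### The first objective concerns all symptomatic survivors, but no stated outcome counts those who leave at consent for lack of access, inability or refusal

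*Combined protocol and SAP*

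**What the plan says.** The Synopsis and section 2.4 both open with the same aim: "To determine if discharged COVID-19 patients with PICS symptoms are willing and able to navigate the technology necessary to participate in a virtual outpatient clinic".

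Section 3.3 sets the order of events. The coordinator reviews the chart, then makes a phone screen. If that shows possible PICS symptoms and mental capacity, verbal consent is sought. Section 2.3.2 then excludes people found during consent to be unable to take part, either because "the patient will not have a home internet connection or smartphone access for the virtual clinic" or because the person "displays the inability to use either a computer or phone for virtual appointments, they will also be excluded from enrollment". Section 2.4.6.6 accepts that others will not join: "all patients meeting criteria consented and participated), however since that is unlikely, a convenience sample will be used".

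The log described in section 2.4.1 is a Day 1 step listed after consent: "RC: Add patient to enrollment log: Study ID, first name, 3 letters of last name, MRN#, hospital discharge date". A consented patient who does not complete the surveys within 7 days and does not respond to calls is "considered an enrollment fail (start of study) or withdrawal from study (repeat surveys), document on enrollment log".

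The patient-level primary outcomes in section 2.4.6.3 are the FIM, IAM and AIM scales, the attendance record, on-time arrivals, and "Number of patient successfully completed online questionnaires after initial training". Section 2.4.6.5 plans descriptive summaries and states no denominator for these outcomes.

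**The concern.** The objective names a population: discharged patients with PICS symptoms. The outcomes are measured in a smaller one: those who have access, can use a device, agree to take part and return the first surveys. Lack of access and inability to use a device bear directly on the word able, and refusal bears on the word willing. These patients are seen by the coordinator and then drop out of view.

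A high attendance figure could therefore be reported as an answer to the first objective when it answers a narrower question. Two hospitals with very different uptake could report the same attendance. If reasons for leaving are not recorded at the call, they cannot be reliably recovered later.

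**Working it through.** **Figures the plan gives.** The only derived number is accrual: 29 ICU discharges in the first month × 0.50 expected to develop PICS = 14.5, which reproduces the stated figure of about 15 per month (section 2.4.6.6). The Synopsis plans 80 patients. No expected technology-exclusion rate, refusal rate, enrollment-failure rate or target feasibility rate is stated, so what follows shows direction, plus size under assumptions.

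**Where patients leave, and whether an outcome counts them.**

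- No access (section 2.3.2): leaves at consent, in no stated outcome.
- Unable to use a device (section 2.3.2): leaves at consent, in no stated outcome.
- Declines (sections 3.3 and 2.4.6.6): leaves at consent, in no stated outcome.
- First surveys not done and calls not answered (section 2.4.1): on the enrollment log, not stated to be a feasibility failure.

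If the last group is left out of the denominator, first-survey completion by any mode is close to 100% by construction, because not completing the surveys is part of what defines the group.

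**Direction.** Let e be the share excluded for access or ability, u the share of the remainder who decline, and f the share of those consenting who become enrollment failures. Counting all three as not served,

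rate among all approached = rate among enrolled × (1 − e)(1 − u)(1 − f).

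The enrolled-only rate is too high by the factor 1/[(1 − e)(1 − u)(1 − f)], which exceeds 1 whenever any loss is above zero.

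**Size, all loss rates assumed.** Suppose 72 of 80 enrolled succeed, which is 90%. The Wilson 95% interval has centre (0.90 + z²/160)/(1 + z²/80) = 0.882 and half-width 0.067 with z = 1.96, so it runs from 81% to 95%. The number approached is 80/[(1 − e)(1 − u)(1 − f)], rounded up.

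| e / u / f | Share retained | Approached | Rate among approached | Factor |
|---|---|---|---|---|
| 5 / 10 / 5% | 0.95 × 0.90 × 0.95 = 0.812 | 99 | 72/99 = 73% | 1.23 |
| 10 / 20 / 10% | 0.90 × 0.80 × 0.90 = 0.648 | 124 | 72/124 = 58% | 1.54 |
| 20 / 30 / 10% | 0.80 × 0.70 × 0.90 = 0.504 | 159 | 72/159 = 45% | 1.98 |
| 30 / 40 / 20% | 0.70 × 0.60 × 0.80 = 0.336 | 239 | 72/239 = 30% | 2.98 |

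The trial would report 90% in every row. All four corrected rates lie below the interval, so the interval gives no warning of the gap.

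**Technology exclusion alone** (u = f = 0). With e = 5%, 10%, 20% and 30%, the rates are 72/85 = 85%, 72/89 = 81%, 72/100 = 72% and 72/115 = 63%. The larger falls in the table need refusal and enrollment failure as well.

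**The case against.** The exclusion is sensible in practice: someone with no connection cannot attend a virtual visit. Consent is unavoidable, and no study observes attendance in people who decline. The convenience sample is openly stated. This stands, and is why the exclusion should stay.

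A reader might infer that ability is tested only in people already known to be able, and willingness only in people who already agreed, so that the result is empty. The documents do not support that. Enrolled patients must still open survey links, reach MyChart or Zoom, arrive on time and complete questionnaires, and they can fail at any of these. Non-response after consent is logged. The Day 1-2 walk-through concerns MyChart access; it is not device training withheld from those excluded.

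A reader might also infer that true uptake would fall inside the range for existing clinics in section 2.1.1, where "Some authors report only 20-50% of patients discharged from the ICU suffering from symptoms, will seek follow-up care at a PICS clinic". That is not supported either. The range is background only, no objective or analysis compares with it, and its base differs: this trial also removes people by chart review and for lack of a contact number. Exclusion for technology alone, at the assumed rates, leaves 63% to 85%, above that range. Declining a research study with repeated surveys is also not the same as declining a virtual clinic.

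Finally, the phone-screen form, consent script and data list are attachments that were not available, so a tally may exist there. Even so, no stated outcome or analysis uses one.

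**Conclusion.** The concern holds in a limited form, as something that should be fixed rather than a fatal flaw. The enrolled-only rates are valid for consenting patients with technology access. As an answer to the first objective they are too favourable whenever any patient is excluded for technology, declines or becomes an enrollment failure.

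The direction follows from the design, provided that those who leave are counted as not served. The size is not in the documents. Over the assumed losses the overstatement is a factor of about 1.2 to 3.0, and those rates are illustrations, not estimates. Whether anything is recorded about patients who leave at consent is unknown; what the text does establish is that no outcome or analysis reports them.

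**What to change.** Keep the eligibility criteria, and make three additions.

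1. **Tally.** At the consent call, record anonymously one category for every patient whose phone screen shows PICS symptoms and capacity: no access, unable to use a device, declined (with the reason), or consented. The consent call is the right place because section 2.3.2 finds technology problems during consent, and section 3.3 puts consent after the phone screen. The reason for declining helps to separate refusal of research from refusal of a virtual clinic.
2. **One primary feasibility outcome**, with all such patients as the denominator: the proportion in each category, the proportion who become enrollment failures, and the proportion who consent and attend the first virtual visit. Enrollment failures count as failures here.
3. **Labels.** Describe primary outcomes 1-4 as applying among consenting patients with technology access. If the 20-50% figure is mentioned in the report, give it as context only, with a note that its base differs.

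The cost is a short tally (the text describes a phone screen but no screening log), one outcome line, and a less favourable headline figure. Visits and the planned 80 patients do not change. The new denominator still omits people removed by chart review, those without a contact number and those who decline the phone screen, and the report should say so.
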